9.7 Imputation of Missing Data

Unless otherwise specified, all data will be evaluated as observed, and no imputation method for missing values will be used.

In all participant data listings, imputed values will be presented, and imputed information will be flagged.

Missing statistics, e.g., when they cannot be calculated, should be presented as "nd". For example, if n=1, the measure of variability (SD) cannot be computed and should be presented as "nd".

Where tables are presented over time, the total number of participants with missing and non-missing observations at each time point should reflect the complete population.

Incomplete or missing start dates of DMDs reported during the Extension Study Period will be imputed as follows:

- In cases where the start date is completely missing the start date will be replaced by M24 Visit + 1
- if start date is partially missing but the start month and year, or the start year are equal to the M24 Visit date then the onset date will be replaced by M24 Visit + 1.
- In all other cases the missing onset day or missing onset month will be replaced by 1st day of the known month or 1st day of the known year.

Incomplete or missing onset dates of relapses reported at Extension Study Baseline Visit (i.e., relapses experienced during gap period) will be imputed as follows:

- In cases where the onset date is completely missing the onset date will be replaced by M24 Visit + 1
- if onset date is partially missing but the onset month and year, or the onset year are equal to the M24 Visit date then the onset date will be replaced by M24 Visit + 1.
- In all other cases the missing onset day or missing onset month will be replaced by 1st day of the known month or 1st day of the known year.

Incomplete or missing onset dates of relapses reported after Extension Study Baseline Visit will be imputed as follows:

- In cases where the onset date is completely missing the onset date will be replaced by the Extension Study Baseline Visit date + 1.
- if onset date is partially missing but the onset month and year, or the onset year are equal to the Extension Study Baseline Visit, then the onset date will be replaced by the Extension Study Baseline Visit date + 1.

• In all other cases the missing onset day or missing onset month will be replaced by 1st day of the known month or 1st day of the known year.

Incomplete or missing onset dates of AE-associated dates during the Extension Study Period will be imputed as follows:

- In case the onset date is missing completely or missing partially but the onset month and year, or the onset year are equal to the M24 Visit date then the onset date will be replaced by the M24 Visit + 1.
- In all other cases the missing onset day or missing onset month will be replaced by 1st day of the known month or 1st day of the known year.
- Incomplete stop dates will be replaced by the last day of the month (if day is missing only), if not resulting in a date later than the date of participant's death. In the latter case the date of death will be used to impute the incomplete stop date.
- In all other cases the incomplete stop date will not be imputed.

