4.1 Overall Design

This will be an open label, single arm, multicenter, retrospective and prospective, 2-year Phase IV extension study of the MAGNIFY MS trial (EudraCT no.: 2017-002631-42).

The parent study (MAGNIFY MS trial) is a single arm, open label, multicenter, 2-year Phase IV study of participants who received treatment with cladribine tablets for 2 years, with one treatment course of 2 weeks each year. Baseline is defined as the day on which the first dose of cladribine tablets was administered.

This extension study involves a 2-year follow-up of participants who completed the parent study. Participants who early withdrew or were withdrawn from treatment with cladribine tablets in the parent study may participate in the extension study. The follow-up period will cover Year 3 and 4 after initial administration of cladribine tablets. During this follow-up period, participants will not be treated with cladribine tablets.

Extension Baseline: The extension Baseline is planned such that it coincides with the last study visit of the parent study (i.e., Month 24 Visit of the parent study). The parent study last visit is planned at 12 months after initiation of the second-year treatment with cladribine tablets (or 24 months after initiation of first year treatment if the participant did not initiate the second-year treatment). For participants who complete the parent study before recruitment is open for the extension study, the extension Baseline visit will be planned later, after the parent study last visit and before Visit 1. For these participants, there will be a gap period between the parent study last visit and extension Baseline. Extension Baseline will involve retrospective data collection for the participants with a gap period between the parent study last visit and extension Baseline, to record any EDSS assessments, relapses, any adverse events (AEs) and serious adverse events (SAEs) (see Section 8.3.1), and concomitant medications (see Section 6.5) that may have been performed/initiated in that time period.

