8.1.3 Relapses

In this protocol, symptoms and signs of relapse or worsening of MS since the previous visit will usually be captured in the context of the efficacy assessment and recorded on the relapse module of the eCRF. Therefore, symptoms, relapses or worsening of MS will not be considered as adverse events (AEs) nor captured on the AE module of the eCRF unless considered possibly or probably related to cladribine tablets (i.e. worsening is not consistent with the anticipated natural progression of the disease).

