14.2 Secondary Endpoints

14.2.1 No Evidence of Disease Activity

As a secondary analysis, NEDA-3 during the following Periods (see definition in Section 9.6) will be analyzed similarly as in the primary analysis using the KM method:

Year 3 Visit Period

- Start date: end date of M24 Visit (see definition in Section 14.1.1) + 1
- Event date: same as in Section 14.1.1 accounting for events started during Year 3 Visit Period only
- Censoring date: the minimum of the scan date of the last available MRI during Year 3 Visit Period, the assessment date of the last available EDSS during Year 3 Visit Period, and the end date of Year 3 Visit Period (see definition in Section 9.6)

Year 4 Visit Period

- Start date: end date of M36 Visit + 1
- Event date: same as in Section 14.1.1 accounting for events started during Year 4 Visit Period only

• Censoring date: the minimum of the scan date of the last available MRI during Year 4 Visit Period, the assessment date of the last available EDSS during Year 4 Visit Period, and the Extension Study completion/discontinuation date

After start of study medication until end of Year 3 Visit Period

- Start date: date of Day 1 as defined in Section 9.5
- Event date: The event date will be defined as the minimum of
 - o the onset date of the first qualifying relapses during the Parent and Extension Study Period
 - o the start date of the first 6MCDP during the Parent and Extension Study Period
 - o the scan date of the first MRI during the Parent and Extension Study Period where at least one T1 Gd+ lesion or at least one active T2 lesion (see Section 9.8 for definition) is identified,

accounting for events started during "After start of study medication until end of Year 3 Visit Period" only.

• Censoring date: the minimum of the scan date of the last available MRI during "After start of study medication until end of Year 3 Visit Period", the assessment date of the last available EDSS during "After start of study medication until end of Year 3 Visit Period", and the end date of "After start of study medication until end of Year 3 Visit Period" (see definition in Section 9.6)

After start of study medication until end of Year 4 Visit Period (i.e. Parent and Extension Study Period)

- Start date: date of Day 1 as defined in Section 9.5
- Event date: same as for "After start of study medication until end of Year 3 Visit Period" accounting for events started during "After start of study medication until end of Year 4 Visit Period"

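### SAP 9.7 sets no floor at the last attended visit, so a relapse first reported after Visit 1 with no onset date is counted in Year 3, although it normally began in Year 4

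*SAP*

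**What the plan says.** SAP 9.7 has two sets of rules for incomplete relapse onset dates. One covers relapses reported at the extension Baseline visit and uses M24 + 1 as the earliest date. The other covers all relapses reported later, with three branches:

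- Fully missing date: "In cases where the onset date is completely missing the onset date will be replaced by the Extension Study Baseline Visit date + 1".
- Partial date that matches extension Baseline ("if onset date is partially missing but the onset month and year, or the onset year are equal to the Extension Study Baseline Visit"): also extension Baseline + 1.
- Any other partial date: "replaced by 1st day of the known month or 1st day of the known year".

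The second set does not distinguish Visit 1, Visit 2 and unscheduled visits.

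Protocol 4.1 places extension Baseline at the parent study's last visit or, for participants with a gap, "after the parent study last visit and before Visit 1". SAP 9.6 ends the Year 3 Visit Period at the M36 (Visit 1) end date and starts Year 4 the next day. SAP 14.2.1 analyses Year 3 NEDA-3 "accounting for events started during Year 3 Visit Period only", and has the matching restriction for Year 4. A participant with no event in the period is censored. On collection, protocol 8.1.3 says that "symptoms and signs of relapse or worsening of MS since the previous visit will usually be captured" in the relapse module.

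For AE onsets that are fully missing, or partial and matching the M24 month or year, SAP 9.7 says "then the onset date will be replaced by the M24 Visit + 1". DMD start dates have an equivalent rule.

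**The concern.** Relapse information is normally gathered for the interval since the last visit. A relapse that first appears at Visit 2 is therefore normally one that began after Visit 1. With the date missing, the rule puts it back into an interval for which the participant had already been seen without reporting it.

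The two year-specific NEDA-3 endpoints then move in opposite directions. Year 3 gains an event that normally belongs to Year 4, and Year 4 loses it. Choosing the earliest date is usually defended as conservative. Here it is conservative for Year 3 and favourable for Year 4.

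The same misplacement reaches:
- the repeats of these analyses in the Course 1 and Course 2 NEDA-3 subsets;
- NEDA-3 from start of medication to the end of Year 3;
- the timing of time to first disease activity, time to first relapse and the mean cumulative function of relapses;
- possibly the interim analysis, because SAP 6.1.1 admits later-reported events whose onset is at or before the cut-off.

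None of the sensitivity analyses in SAP 14.1.2 varies the date imputation.

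**Working it through.** The plan gives no figure on this point, so there is none to reproduce.

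**Inputs.** Visit 1 is at M24 + 360 days and Visit 2 at M24 + 720 days (SAP 9.5). The planned evaluable number is 200 to 220 (protocol synopsis). The imputation rules are those of SAP 9.7. Assumed: true onset is uniform between Visit 1 and Visit 2, gaps run from 0 to 350 days, and extension Baseline dates are spread over a calendar year.

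**Step 1: an example.** M24 and extension Baseline 15 Jun 2021, Visit 1 10 Jun 2022, Visit 2 5 Jun 2023. True onset 1 Dec 2022, first reported at Visit 2.

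| What is recorded | SAP 9.7 date | Period | Date with a floor at Visit 1 + 1 | Period |
|---|---|---|---|---|
| Nothing | 16 Jun 2021 | Year 3 | 11 Jun 2022 | Year 4 |
| 2022 | 1 Jan 2022 | Year 3 | 11 Jun 2022 | Year 4 |
| Dec 2022 | 1 Dec 2022 | Year 4 | 1 Dec 2022 | Year 4 |

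**Step 2: share of true Year 4 onsets placed in Year 3.**
- Fully missing: extension Baseline + 1 is not later than Visit 1, so 100% at every gap length tried.
- Year only: misplaced when onset falls in the same calendar year as Visit 1. On average about half a year remains after Visit 1, so 182.5/360 = 51%. Applying the rule to simulated dates gave 50% to 51%.
- Month and year: misplaced when onset falls in the same month as Visit 1. On average half a month remains, so (30.4375/2)/360 = 4.2%. Simulated dates gave 3.9% to 4.2%.

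**Step 3: distance moved, fully missing date.** With no gap, the imputed day is M24 + 1 and the true day lies between M24 + 361 and M24 + 720. The date moves 361 - 1 = 360 to 720 - 1 = 719 days earlier. A gap of g days reduces both figures by g.

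**Step 4: effect on the one-year proportions.** For k misplaced relapses in participants with no other event in either year, and ignoring censoring, the shift is 100 × k/N points, down in Year 3 and up in Year 4.
- k = 1: 100/220 = 0.45 to 100/200 = 0.50 points.
- k = 5: 500/220 = 2.27 to 500/200 = 2.50 points.

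**Step 5: effect on the primary analysis.** The event stays inside the Extension Study Period, so two-year event status does not change. Only its time moves. A simulation with assumed values (N = 210, 20% with an event in each year, 10% dropout, 300 runs, events moved to the start of the curve) raised the 24-month Kaplan-Meier estimate by 0.03 points on average for one case (range 0.01 to 0.08). For five cases it rose by 0.17 points (0.06 to 0.31).

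**The case against.** The strongest reply is that the trigger is rare. A qualifying relapse must be separated by at least 30 days from the onset of a preceding event (protocol 8.1.3.1), so its onset has to be roughly known. Participants are told to make contact at once, and examination follows within 7 days of the report once fever or infection is excluded (8.1.3.2). SAP 14.1.1 itself speaks only of partial onset dates. This stands: fully missing dates should be few, and month-and-year dates are seldom misplaced.

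Second, onset after Visit 1 is not certain. Protocol 8.1.3 says only that capture since the previous visit is usual, and SAP 6.1.1 provides for events reported later with an earlier onset. This also stands, so the lower bound is the normal case and not a fact about every relapse.

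Third, earliest-date imputation is a common convention, imputed dates are flagged in listings, and the study is exploratory with one arm. That limits the weight of the point but does not justify the allocation. SAP 9.7 already separates reports at extension Baseline from later ones and raises the floor accordingly. It stops one visit short.

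A reader might also infer more than the documents support:
- That the rule takes no account of the reporting visit. It does so once, at extension Baseline.
- That every case is both a false Year 3 failure and a false Year 4 success. The Year 3 failure is false only if there is no other Year 3 event. Year 4 loses an event only if there is no other there, such as MRI activity at M48, and the participant is then censored, not recorded as a success.
- That events pile up on day 1 of the primary curve. That happens only without a gap, because the curve starts at M24 + 1 and the imputed relapse date is extension Baseline + 1.
- That DMD and AE results are distorted in the same way. Time to DMD start has no year-specific endpoint. A misdated AE shortens one person's time at risk but still counts over the whole extension period (SAP 15.1.1).

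**Conclusion.** The point holds for the year-specific analyses. As written, SAP 9.7 moves a relapse first reported after Visit 1 from Year 4 to Year 3 whenever its onset date is fully missing, and about half the time when only the year is known. Nothing elsewhere in the plan corrects this. The direction is always the same: Year 3 NEDA-3 is understated and Year 4 NEDA-3 overstated. The size is that of step 4 for each affected participant.

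This rests on onset after Visit 1 being the normal case, on a uniform spread of onsets for the year-only and month-and-year shares, and on no other event in the period concerned. The documents do not give the number of incomplete dates. The primary conclusion is not threatened: event status over the two years is unchanged, and the 24-month estimate moves only slightly under the assumed rates. This is a small but systematic error in named secondary endpoints, worth correcting before the final analysis.

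**What to change.** Amend the SAP 9.7 rule for relapses reported after extension Baseline as follows.

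- **Fully missing onset, or a partial date whose known month or year includes or follows the last attended visit before the report:** impute the later of (a) the first day of the known month or year, if any, and (b) the day after that visit's end date. For a first report at Visit 2 after an attended Visit 1, (b) is the first day of the Year 4 Visit Period.
- **Recorded month or year wholly before that visit:** keep it and apply the existing rule. A genuine late report is then not overwritten by the floor.

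Where the last attended visit is extension Baseline, fully missing dates are imputed as now.

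Apply the same floor to DMD start and AE onset dates, in place of M24 + 1, only if the sponsor confirms that the reporting visit or entry date is available for those eCRF pages. The documents do not show that it is.

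The cost is a few lines of SAP text and a small programming change. For relapses, the existing split between reports at and after extension Baseline already requires the reporting visit to be identifiable. A count of relapses with imputed onset, by type of missing date and reporting visit, would show whether the matter is of any size.

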9.2 Definition of Visit Dates

The visit start date is the date of the first assessment which belongs to the corresponding visit.

The visit end date is the date of the last assessment which belongs to the corresponding visit.

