9.5 Time Window

- Day 1 is the day of start of study medication at MAGNIFY MS Baseline Visit, the day before is Day -1 (no Day 0 is defined).
- Study day is defined relative to Day 1.

The visit schedule in the Extension Study is defined as follows:

- 1 month = 30 days,
- 1 year = 360 days,

relative to the M24 Visit in the parent study.

- MAGNIFY Extension Baseline Visit: The visit is planned to coincide with or be as near to M24 as possible to minimize the transition gap period, it may also be the same visit as M24.
- Visit 1: 1 year ((360 days) after M24 Visit (\pm 30 days)
- Visit 2: 2 years (720 days) after M24 Visit (± 30 days)

Visit 1 and Visit 2 will also be referred to as the M36 Visit and the M48 Visit, respectively, in the following sections of this IAP as well as in the Tables, Listings, and Figures (TLF) outputs, for consistent presentation of analyses and results over time. Footnotes will be added in the TLF outputs to clarify that these Visits are to be understood as nominal Visits.

In each analysis, should an assessment be delayed, participants' assessment data will be treated as though it occurred at the nominal time point specified (i.e., data collected out of visit windows will not be excluded or adjusted in any analysis) and inferences will be conducted accordingly. Thus, further time windows will not be specified. The MRI assessment will be the only exception to this rule. Handling of out-of-window MRI assessments is discussed in Section 9.8.

All observations from unscheduled visits will be included only in the analyses of visit independent summaries (e.g., counts of AEs, concomitant medications and procedures, relapse reporting and EDSS) unless for the last assessment available. In this case the missing Early Withdrawal (EW) visit will be imputed by the unscheduled visit.

The assessments of the EW visit will be mapped to the nearest planned post-baseline visit with a missing assessment before or after the EW visit of the individual assessment for all statistical analyses and descriptive summaries. As not all assessments of the EW are performed at each visit, the different assessments of the EW can be assigned to different visits. If the duration (in days) between the EW visits and two missing planned visits are equal, then the assessment will be assigned to the later visit.

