9.6 Study Period

Study Periods

The following study periods are defined:

Treatment Period (i.e., Parent Study Period): see MAGNIFY MS IAP version 3.0 for definition.

Course 1 Treatment Period: see MAGNIFY MS IAP version 3.0 for definition.

Course 2 Treatment Period: see MAGNIFY MS IAP version 3.0 for definition.

Gap Period:

- Start = Visit end date of M24 Visit + 1
- End = Extension Study Baseline Visit start date

Year 3 Visit Period:

- Start = Visit end date of M24 Visit + 1
- End = Visit end date of M36 Visit

Year 4 Visit Period:

- Start = Visit end date of M36 Visit + 1
- End = Visit end date of M48 Visit

Year 3 Visit and Year 4 Visit Period (i.e., **Extension Study Period**):

- Start = Visit end date of M24 Visit + 1
- End = Visit end date of M48 Visit

After start of study medication until end of Year 3 Visit Period:

- Start = Start of study medication (see MAGNIFY MS IAP version 3.0 for definition)
- End = Visit end date of M36 Visit

After start of study medication until end of Year 4 Visit Period (i.e., **Parent and Extension Study Period**):

- Start = Start of study medication (see MAGNIFY MS IAP version 3.0 for definition)
- End = Visit end date of M48 Visit

In case of missing M48 Visit or early discontinuation before an End of Period defined above, the Visit end date of EW Visit will be used to replace the corresponding End date, or the study discontinuation date will be used if the EW visit was not performed.

In case of missing M36 Visit, the Visit end date of M36 Visit in the above definitions (including Start and End) will be replaced by MAGNIFY MS M24 Visit date + 480 days (which is obtained by 360 (12 months) + 90 (3 months delay allowed for FAS) + 30 (Visit window)), or the Visit end date of EW Visit if earlier, or date of discontinuation if earlier and the EW Visit was not performed.

Study Periods for MRI Assessments

The MRI scans in the parent study were reconciled during central MRI review process. Therefore, MRIs were considered as Baseline MRIs if assigned to the Baseline Visit by the central imaging review.

The following study periods for MRI assessments are defined as per MAGNIFY MS IAP version 3.0 with extension to Month 36 Visit and Month 48 Visit MRI scans:

Baseline Period (p₀): The Baseline Period is defined as the Period between the Screening and the Baseline MRI scan in MAGNIFY MS trial.

Post-Baseline Periods (ppost-Baseline):

Yearly Periods:

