14.1.1 Primary Objective: Derivation and analysis of the primary endpoint

No Evidence of Disease activity (NEDA), also referred to as freedom from disease activity, is a new goal that is emerging in MS treatment. NEDA is a composite measure of disease activity, including relapses, cognition and disability progression, and MRI activity.

NEDA-3 during the Extension Study Period is defined as absence of the following three events during the Period:

- Qualifying Relapses
- 6-months Confirmed Disability Progression (6MCDP, see definition below)
- MRI Activity (i.e., presence of T1 Gd+ lesions and/or active T2 lesions)

NEDA-3 will be analyzed with the Kaplan-Meier (KM) time-to-event method to reduce the impact of unknown/missing information.

The start date will be the end date of M24 Visit + 1.

The event date will be defined as the minimum of

- the onset date of the first qualifying relapses during the Extension Study Period
- the start date of the first 6MCDP during the Extension Study Period (see definition below)
- the scan date of the first MRI during the Extension Study Period where at least one T1 Gd+ lesion or at least one active T2 lesion (see Section 9.8 for definition) is identified.

Imputation of partial onset dates of relapses is described in Section 9.7. Since full dates of MRI scan and EDSS assessment are mandatory, partial dates of 6MCDP, or MRI Activity are not expected.

If the participant did not experience any of the three events described above during the Extension Study Period, the minimum of the scan date of the last available MRI, the assessment date of the last available EDSS, and the Extension Study completion/discontinuation date will be used as the censoring date.

The time to disease activity (in months) will be calculated as [event date or censoring date as applicable – start date + 1]/30.4375. The number of participants at risk, failed, and survival rate (i.e., the proportion of participants with NEDA-3) along with the 95% CI will be estimated as per the KM method and reported at 6-months intervals. The KM survival curve will be plotted as well.

A descriptive summary of number and proportion of participants with event (overall and by type of event, i.e., qualifying relapse, 6MCDP, or MRI activity as the earliest event) and censored will be also presented.

6MCDP

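### SAP 9.7 does not hold imputed onset dates consistently at the start of the Extension Study Period, so a late-reported gap-period relapse can be dated before it and leave the primary NEDA-3 analysis

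*SAP*

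**What the plan says.** SAP 9.6 opens the Extension Study Period, the Gap Period and the Year 3 Visit Period alike with "Start = Visit end date of M24 Visit + 1". SAP 9.2 adds that "The visit end date is the date of the last assessment which belongs to the corresponding visit", so M24 may end on a later day than it began. In SAP 14.1.1 the relapse part of the primary event date is "the onset date of the first qualifying relapses during the Extension Study Period".

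SAP 9.7 then treats incomplete dates in four blocks:

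- **DMD starts.** "In cases where the start date is completely missing the start date will be replaced by M24 Visit + 1". The same date is used "if start date is partially missing but the start month and year, or the start year are equal to the M24 Visit date".
- **Relapses reported at Extension Baseline.** A fully missing onset goes to M24 plus one day, and so does a partial one "if onset date is partially missing but the onset month and year, or the onset year are equal to the M24 Visit date".
- **AE onsets.** These follow the same pattern, anchored on M24.
- **Relapses reported after Extension Baseline.** If the date is "completely missing the onset date will be replaced by the Extension Study Baseline Visit date + 1". A partial date gets that same value if its month and year, or its year, match those of Extension Baseline. It is not compared with M24.

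In every block, any other partial date goes to the first day of the known month or year.

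SAP 9.5 says of the Extension Baseline Visit that "it may also be the same visit as M24". Protocol 4.1 allows it to fall later, and SAP 10.1 tabulates gaps up to more than 12 months.

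**The concern.** The primary analysis counts a relapse only if its onset date lies inside the Extension Study Period. An imputed date even one day too early removes a relapse that did occur in the Period. The same relapse is lost from time to first qualifying relapse and from the mean cumulative function, both counted from M24 (SAP 14.2.3).

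The descriptive rule in SAP 14.1.1 turns on whether a relapse was reported in the Period, not on its onset. One participant could therefore be event-free in the Kaplan-Meier analysis and a Yes in the component table. In the crude proportion, losing a relapse can only raise NEDA-3 or leave it unchanged.

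Incomplete gap dates are plausible. Protocol 4.1 collects gap relapses retrospectively, and Protocol 8.1.8 issues the diary only at the Baseline Visit.

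**Working it through.** The plan gives no figure to reproduce, so the check applies the rules to dates.

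**1. Anchors against the Period start (SAP 9.6 and 9.7)**

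| Block | Partial date compared with | Lower bound when matched or fully missing |
|---|---|---|
| DMD starts | M24 | M24 plus 1 day |
| Relapses reported at Extension Baseline | M24 | M24 plus 1 day |
| AE onsets | M24 | M24 plus 1 day |
| Relapses reported after Extension Baseline | Extension Baseline only | Extension Baseline plus 1 day |

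The Period starts at the M24 visit *end* date plus 1 day. No block names that date.

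**2. Gap relapse reported late**

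Illustrative inputs: M24 ends 20 Nov 2020, the Period starts 21 Nov 2020, Extension Baseline is 10 Feb 2021, and the relapse is first reported at Visit 1.

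- Onset known as 2020: no match with 2021, so it becomes 1 Jan 2020, 325 days before the start. Time = event − start + 1 = −324 days.
- Onset known as Nov 2020: no match, so it becomes 1 Nov 2020, 20 days before the start. Time = −19 days.
- Had the same relapse been reported at Extension Baseline, both onsets would match M24 and become 21 Nov 2020 (with M24 read as its end date). That is inside the Period, with time = 1 day.

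One relapse thus gets two dates depending only on when it was reported. Neither year nor month matches Extension Baseline here, so the result does not depend on how the year-only match is read.

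**3. M24 over several days**

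Illustrative inputs: Extension Baseline coincides with M24 on 10 Mar 2021, the last M24 assessment is on 14 Mar, and the Period starts 15 Mar. A fully missing onset reported later becomes 11 Mar 2021. Time = 11 − 15 + 1 = −3 days.

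The schedule (Protocol Table 2) has no MRI at Extension Baseline, so an M24 scan on a later day could produce this. Protocol 8.1 allows ±5 days between extension assessments; the parent-study window is not in the documents. The M24-anchored rules have the same weakness if their M24 date is read as the visit start.

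**4. How often, under assumed dates**

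The rules were applied literally to simulated onsets, uniform over 720 days from the Period start. Assumed: M24 between mid-2019 and late 2021, gaps of 0 or 10 to 329 days, and M24 lasting one day or ending 5 days after it began. Share of imputed dates before the Period start:

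| Situation | Day missing | Day and month missing | Fully missing |
|---|---|---|---|
| M24 rules, M24 read as its end date | 0 | 0 | 0 |
| Reported after Extension Baseline, onset after it | 0 | 0 | 0 |
| Reported after Extension Baseline, onset in gap | 8.3–8.7% | 32.3–32.8% | 0 |
| DMD/AE rules, M24 read as its start, ending 5 days later | 2.0% | 23.8% | 100% |

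The simulation never placed Extension Baseline before the end of M24, so it does not cover the case in step 3.

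**5. Size per relapse**

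Protocol 1.1 plans 200 to 220 evaluable participants. One relapse lost as a participant's only event moves the crude proportion by 1/220 = 0.45 to 1/200 = 0.50 percentage points.

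**The case against.** A reader might infer that SAP 9.7 imputes relapse, DMD and AE dates with no floor at all. The text does not support that. Three of the four blocks have an explicit bound at M24 plus one day, and the fourth has one at Extension Baseline plus one day. With M24 read as its end date, the M24 rules never dated an event before the Period. The label on the gap-relapse block also suggests that all gap relapses were meant to take the M24 bound.

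The remaining cases are narrow. A gap relapse must be missed by the retrospective collection at Extension Baseline, surface later, still qualify, and have a partial date of the wrong kind. Protocol 8.1.3 requires objective impairment, and examination within 7 days of reporting once fever or infection is excluded, so a fully undated qualifying relapse is unlikely. The M24 anchor is ambiguous rather than wrong, and SAP 9.6 supplies a consistent reading.

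A reader might also take the year-match clause to overwrite known months. The natural reading is that the year alone is compared only when the month is missing too. Nor do the documents allow a count of exposed relapses: they give neither the number of relapses nor the share with incomplete dates, and most incomplete dates would be unaffected.

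One lost relapse is also small beside sampling error. At n = 200 and an assumed proportion of 0.5, the 95% half-width is 1.96 × √(0.25/200) = 6.9 points, and the study tests no formal hypothesis. Such a relapse would still enter the analyses counted from first dose, though at too early a date.

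All of this limits frequency and size. It does not remove the rule in working step 2, which gives a wrong date when followed as written.

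**Conclusion.** The point holds in a narrow form. A partially dated gap relapse reported after Extension Baseline can be placed before the Extension Study Period and lost from the primary Kaplan-Meier NEDA-3 and the relapse analyses from M24. Separately, the plus-one-day anchors can precede the Period start when M24 spans more than one day; for the M24 anchor this needs M24 to be read as the visit start.

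The effect is probably rare and small, at 0.45 to 0.5 points of crude NEDA-3 per relapse lost as a sole event. The shares in working step 4 depend on assumed date and gap distributions. It is worth correcting because the crude error runs in one favourable direction on the primary endpoint.

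**What to change.** In SAP 9.7:

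1. Replace the M24-plus-one anchor by the M24 visit end date plus one day throughout, to agree with SAP 9.6.
2. For relapses, DMDs and AEs recorded in the extension, set imputed date = max(date by rule, M24 visit end date + 1). Apply this only if the date is completely missing or its known parts allow an onset on or after that day.
3. Leave unchanged any event whose known month or year lies wholly before M24. Without this limit, and with M24 ending 20 Nov 2020, an event dated Jun 2020 would be moved to 21 Nov 2020 and become a false extension event.
4. As a clarification only, state that the year-only match applies when the month is also missing.

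Under this change both onsets in working step 2 become 21 Nov 2020, and the one in step 3 becomes 15 Mar 2021. The cost is a few sentences in the SAP and a small change to the derivation code, with no new data.
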